16.5.2 Tuberculosis Assessments

After initial TB assessments are carried out at screening, QuantiFERON-TB Gold tests are carried out at Weeks 24 and Week 52 during the study.

Completion status (done/not done) and result (negative/positive) will be summarized by visit and treatment arm.

16.6 Safety/ADA Correlation Analysis

The following frequency tables by treatment arm, status of ADA (negative or positive, where positive is defined as at least one positive result post-dose), primary SOC and PT will be provided for:

[figure not shown]
- TEAEs
- AESIs (Hypersensitivity)
- Injection Site Reactions

The tables will be repeated for neutralizing antibody positive versus negative status.

[figure not shown]
17 Reporting Conventions and Data Handling

[figure not shown]
The reporting conventions will follow those detailed in the Biostatistical Output Assembly (BOA) v2.0 document.

19 References

- FDA, Guidance for Industry RA: Developing Drug Products for Treatment, 2013.
- Ware JE Jr and Sherbourne CD. The MOS 36-item short-form health survey (SF-36). I. Conceptual framework and item selections. Med Care. 1992; 30(6):473-483.

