### 3.3 Safety and tolerability

The expected safety profile for MSB11022 is that known for EU-approved and US-licensed Humira®. The exclusion criteria for this trial take the known side-effect profile for adalimumab into consideration.

Adalimumab is known to compromise host defenses against pathogenic organisms, resulting in possible reactivation of tuberculosis (TB), invasive fungal infections, or susceptibility to opportunistic pathogens such as Legionella or Listeria. Upper respiratory tract and pulmonary infections feature prominently within the AE profile (12, 13, 14, 15, 16, 17, 18). Explicit screening for TB before exposure to Humira® is included in the trial procedures. No serious infections were reported in the first-in-human Trial EMR200588-001.

Minor differences in structural features such as glycosylation profiles cannot be excluded between 2 batches of closely related biological molecules targeting the same cell functions. For most biological systems, such minor variations is not expected to adversely impact the compound's ability to perform the biological role. In contrast, the immune system is uniquely sensitive to small biological variations and has the ability to distinguish between almost identical molecular entities. Accordingly, immunogenicity, such as anti-drug antibodies (ADAs), will be measured in this trial, and the results will be compared between the trial treatment arms. Differences in immunogenicity as ascertained in highly sensitive laboratory experiments may be indicative of a difference in the propensity to trigger clinically meaningful reactions of the immune system, eg, injection site reactions, or other forms of hypersensitivity (19).

The nonclinical pharmacodynamics properties of MSB11022 were investigated in vitro using binding and functional assays, which supported similarity of MSB11022 to Humira®. In addition, a comparative repeat-dose toxicity study was performed in a relevant animal model (cynomolgus monkeys), which proved comparability between MSB11022 and Humira®. Please refer to the current IB for complete nonclinical data.

MSB11022 was found to be equivalent in terms of PK to EU-approved Humira® and US-licensed Humira® and to have a comparable safety profile in Trial EMR200588-001.

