### 8.5.3.5 Analysis of Immunogenicity Endpoints

Descriptive statistics of the immunogenicity assessment per treatment arm will be given with reference to the Safety Analysis Set unless otherwise specified in the SAP.

- Number and percentage of ADA positive patients at any time
- ADA titer
- Number and percentage of NAb positive patients
- Time to ADA
- Change of titer over time
- Persistent or transient ADA for patients with a treatment period  $\geq$  6 months

Presentations will include summaries of PK, safety, and efficacy endpoints over time for ADA positive and negative patients.

Correlation of PK, safety, and efficacy endpoints versus treatment group split by upper and lower quartile patients, based on their maximum ADA titer values, may be presented as exploratory analyses.

ADA status, titer, and NAb status will be listed and summarized by treatment and time point of collection.

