15.3.2 Immunogenicity Analysis

Immunogenicity data will be summarized by treatment arm for the SAF analysis set. Overall ADA status (negative or positive, where positive is defined as at least one positive result post-dose) will be summarized as well as ADA titers and presence or absence of neutralizing antibodies.

Time to positive ADA status, calculated from Trial Day 1, will also be analyzed. Subjects who discontinued the study or were lost to follow-up, or had not reached the endpoint of interest at the time of analysis, will be censored at the date of last sample collection. Results will be summarized by means of Kaplan-Meier curves together with a summary of associated statistics (median, 95% confidence interval) and the number of subjects under risk.

Summary statistics will be presented for the actual titer values, by treatment arm and visit up to Week 52. Boxplots will be produced to present the ADA titer results graphically. The boxplots will present Q1, Q3, median, minimum and maximum.

The number and percentage of ADA positive and NAb positive subjects will be presented for each visit up to Week 52.

The analysis exploring the correlation between ADA and efficacy, PK and safety will be described in Sections 15.3.2.1, 15.3.3.1, and 16.6 respectively.

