16.1 Adverse Events

Adverse events will be collected throughout the study and coded using version 19.1 of MedDRA or later.

Treatment-emergent adverse events (TEAEs) are those events that start on or after the day of first administration of study treatment. If an AE started on the same date as the first administration of the first study treatment given, the timing related to study treatment as recorded on the adverse events page of the eCRF will be taken into account when determining treatment emergence. A worst case approach will be used, ie if time is missing or if the AE occurred at the same time as the first administration of the first study treatment given, then the AE will be classified as treatment-emergent.

Incomplete AE-related dates will be handled as follows:

- In case the onset date is missing completely or missing partially but the onset month and year, or the onset year are equal to the start of study treatment then the onset date will be replaced by the minimum of start of study treatment and AE resolution date.
- In all other cases the missing onset day or missing onset month will be replaced by 1.
- Incomplete stop dates will be replaced by the last day of the month (if day is missing only), if not resulting in a date later than the date of subject's death. In the latter case the date of death will be used to impute the incomplete stop date.
- In all other cases the incomplete stop date will not be imputed.

Only TEAEs will be included in tables and will be summarized by treatment arm. All AEs will be listed.

Unless otherwise stated, TEAEs will be displayed in terms of frequency tables: primary SOC in alphabetical order, then PT in order of decreasing frequency across both treatment arms. If a subject has more than one event for a particular SOC or PT, then the event will be counted once only for the subject. For example, if a subject has two different TEAEs but these are within the same SOC, then they will be counted once for each PT but only once for the SOC. If at any time a summary is being prepared on data that are not fully coded, uncoded TEAEs will be summarized with a SOC as 'Uncoded' and the PT term will be set to the TEAE verbatim text.

If an AE is reported for a given subject more than once during treatment, the worst relationship to study treatment will be tabulated.

Adverse events related to study treatment are those events with relationship missing, unknown or yes.

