16.1.1 All Adverse Events

An overall summary table will present the number of subjects with at least one of the following TEAEs, summarized by treatment arm:

- TEAE
- Study drug related TEAE
- Serious TEAE
- Study drug related serious TEAE
- TEAE of NCI-CTCAE toxicity Grade 1
- TEAE of NCI-CTCAE toxicity Grade 2
- TEAE of NCI-CTCAE toxicity Grade 3
- TEAE of NCI-CTCAE toxicity Grade 4
- TEAE of NCI-CTCAE toxicity Grade 5
- TEAE of NCI-CTCAE toxicity Grade ≥ 3
- TEAE of NCI-CTCAE toxicity Grade ≥ 4
- Study drug related TEAE of NCI-CTCAE toxicity Grade 1
- Study drug related TEAE of NCI-CTCAE toxicity Grade 2
- Study drug related TEAE of NCI-CTCAE toxicity Grade 3
- Study drug related TEAE of NCI-CTCAE toxicity Grade 4
- Study drug related TEAE of NCI-CTCAE toxicity Grade 5
- Study drug related TEAE of NCI-CTCAE toxicity Grade ≥ 3
- Study drug related TEAE of NCI-CTCAE toxicity grade ≥ 4
- TEAE of special interest
- TEAE of special interest Grade 1
- TEAE of special interest Grade 2
- TEAE of special interest Grade 3
- TEAE of special interest Grade 4

- TEAE of special interest Grade 5
- Study drug related AESI
- Study drug related AESI Grade 1
- Study drug related AESI Grade 2
- Study drug related AESI Grade 3
- Study drug related AESI Grade 4
- Study drug related AESI Grade 5
- TEAE leading to death
- Study drug related TEAE leading to death.
- Injection Site Reactions

Incidence rates will be included in these overall summaries as the number of events per 100 subject-years of exposure to IMP, calculated as the number of subjects with AEs divided by the total time at risk across all subjects in the given treatment arm, multiplied by 100. Time at risk for a subject is calculated as time from first dose to 28 days following the last dose of IMP. Two-sided 95% CIs for incidence rates will be provided using the exact Poisson method.

The following frequency tables will be prepared by treatment arm, primary SOC in alphabetical order, then PT in order of decreasing frequency across both treatment arms:

- TEAEs
- Study Drug related TEAEs
- Serious TEAEs
- Non-serious TEAEs with frequency of $\geq 5\%$ in any treatment arm
- Non-serious TEAEs with frequency of $\geq 1\%$ in any treatment arm
- TEAE leading to death
- Study drug related TEAE leading to death
- TEAEs by NCI-CTCAE toxicity grade
- Study Drug related TEAEs by NCI-CTCAE grade
- TEAEs by worst NCI-CTCAE toxicity grade.
- Injection Site Reactions- Local Tolerability

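### SAP 16.6 splits adverse events by ever-positive ADA status without using event onset or follow-up time, so events before antibody detection cannot be told from events after it, and the association can be biased either way

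*SAP*

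**What the plan says.** SAP 16.6 plans frequency tables for TEAEs, hypersensitivity AESIs and injection site reactions by treatment arm and "status of ADA (negative or positive, where positive is defined as at least one positive result post-dose), primary SOC and PT". It adds: "The tables will be repeated for neutralizing antibody positive versus negative status".

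The events that enter are defined in SAP 16.1: "Treatment-emergent adverse events (TEAEs) are those events that start on or after the day of first administration of study treatment". If a subject has several events under one SOC or PT, "then the event will be counted once only for the subject".

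The antibody date is used elsewhere, on its own. SAP 15.3.2 states: "Time to positive ADA status, calculated from Trial Day 1, will also be analyzed". Rates per 100 subject-years are planned in SAP 16.1.1, but only for the overall summary by arm, "calculated as the number of subjects with AEs divided by the total time at risk across all subjects in the given treatment arm". The timing of injection site reactions in 16.1.1 is measured from injections, not from the first positive sample.

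Protocol 3.3 explains why antibodies are measured: a difference in immunogenicity "may be indicative of a difference in the propensity to trigger clinically meaningful reactions of the immune system, eg, injection site reactions". Protocol 8.5.3.5 says: "Presentations will include summaries of PK, safety, and efficacy endpoints over time for ADA positive and negative patients". SAP section 9 declares no change from the protocol.

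**The concern.** The question behind the tables is one of time order: do reactions follow the appearance of antibody? An event that began before any antibody was present cannot answer it. Each adverse event has an onset date and each ADA sample has a date, yet no rule in SAP 15.3.2, 16.1 or 16.6 puts the two in order.

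Two separate errors follow.

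- **Onset is ignored.** Reactions before detection sit in the ADA-positive column. If antibody raises the risk only after it appears, this pulls the two columns together.
- **Follow-up is ignored.** Ever-positive status depends on how long a subject was observed. Longer follow-up gives more samples that could be positive and more time for events, so the two become associated even with no link. SAP section 8 ends the final-analysis data for subjects who stop treatment early at theoretical Week 52 or at the 4-month visit, whichever is first, so follow-up will differ between subjects.

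At stake is whether a reader of the study report can interpret the ADA–safety tables in either arm.

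**Working it through.** **Figures in the plan.** The documents give none for the ADA–safety analysis. The only stated precision is in Protocol 8.1: 12.0% and 9.0% for incidences of 26% and 11%. With 100 per arm, 1.96·√(2·0.26·0.74/100) = 12.16% and 1.96·√(2·0.11·0.89/100) = 8.67%, which match to the whole percent. They do not bear on this point.

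**Inputs from the documents.** Injection site reaction incidence 26%, drop-out 20% and 130 per arm (Protocol 8.1). Samples at Weeks 2, 4, 12, 24, 36 and 52 (Protocol 5.2 for PK; the immunogenicity row of Table 1 has the same pattern). The longest gap is 52 − 36 = 16 weeks.

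**Assumptions not in the documents.** ADA incidence, ADA timing, the shape of the reaction hazard, and the effect of antibody on reactions.

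**Benchmark.** If subjects were positive from day 0 and the risk without antibody is 26%, a hazard ratio of k gives a risk ratio of (1 − 0.74^k)/0.26:
- k = 2: (1 − 0.5476)/0.26 = 1.74
- k = 3: (1 − 0.4052)/0.26 = 2.29

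**Simulation A.** 1,000,000 subjects per scenario; 20% or 40% ADA-positive by Week 52, half of them by Week 12; 20% drop-out; reaction hazard either constant or with half of it in the first 8 weeks. The SAP 16.6 contrast is the risk in ever-positive subjects divided by the risk in the rest. The alternative classifies status at event onset and stratifies by study period.

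| True hazard ratio after seroconversion | SAP 16.6 risk ratio | Risk ratio if positive from day 0 | Status-at-onset rate ratio |
|---|---|---|---|
| 1 | 1.05–1.09 | 1.00 | 1.00 |
| 2 | 1.42–1.64 | 1.74 | 1.91–1.97 |
| 3 | 1.72–2.07 | 2.29 | 2.75–2.91 |

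With no link, 48% (constant hazard) to 66% (early hazard) of first reactions in the ADA-positive column begin before the first positive sample.

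**Simulation B, to test direction.** 200,000 subjects per scenario; onset of ADA uniform over 12, 24 or 52 weeks; an early-termination sample is taken.

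| Scenario | SAP 16.6 risk ratio | Benchmark |
|---|---|---|
| True ratio 2, 40% ADA, full follow-up | 1.25–1.67 | 1.74 |
| No link, 40% ADA over 52 weeks, full follow-up | 1.00 | 1.00 |
| No link, 20% drop-out, 40% / 80% ADA over 52 weeks | 1.11 / 1.31 | 1.00 |
| True ratio 1.2, 20% drop-out, 40% / 80% ADA over 52 weeks | 1.22 / 1.40 | 1.17 |
| No link, half of reactors withdraw at the event | 0.78 | 1.00 |
| True ratio 2, half of reactors withdraw at the event | 1.14–1.20 | 1.74 |

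The no-link rows with constant hazard show the cause. With full follow-up the ratio is 1.00; 20% drop-out alone raises it to 1.11.

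**Does status at onset repair it?** In simulation B, where reactions do not themselves cause withdrawal, true ratios of 1, 1.2 and 2 are recovered as 0.98–1.01, 1.16–1.21 and 1.81–2.00. If half of reactors withdraw at the event and are sampled only then, it gives 1.19 for a true 1 and 2.36–2.38 for a true 2. The rule for such samples therefore matters.

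**The case against.** **The tables are supportive, and the comparison of arms does not rest on them.** This stands. The primary analysis compares hypersensitivity by arm whatever the ADA status, the overall summary gives rates by arm, time to ADA is shown by arm, and the study is declared descriptive. Subject listings also let a reader check dates by hand. But a listing is not an analysis, and the tables will be read for the purpose given in Protocol 3.3.

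**A reader might infer that every true link is diluted, so that the tables always favour a reading of no concern.** The documents do not support that. Nothing in them fixes the direction: drop-out can create a link or exaggerate a weak one, as simulation B shows.

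**A reader might set a hazard ratio of 3 against a risk ratio of 1.7–2.1 and call all of the gap dilution.** Those are different scales. The fair comparison is with 2.29.

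**A reader might infer that SAP 16.6 contradicts the protocol.** Protocol 8.5.3.5 promises a time axis, which the 16.6 tables lack. But it splits patients, not events, and itself counts patients who were positive at any time. It does not promise status at onset.

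**The yield is small.** This also stands. At 20% ADA, 130 × 0.20 = 26 positive subjects per arm, of whom 26 × 0.26 ≈ 7 have a reaction; splitting at first positivity leaves about 3 or 4 on each side. At 40% there are about 14 before the split.

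**First positive sample is not first antibody.** True. A reaction after seroconversion but before the next sample would move to the negative side, which is itself dilution.

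The output shells are not part of the two documents, so table layout cannot be confirmed.

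**Conclusion.** The point holds in this form: the SAP 16.6 tables cannot separate events before antibody detection from events after it, and the association they show can be biased in either direction. This follows from a stated rule, not from missing detail.

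The size depends on assumed ADA incidence and timing. With 20–40% positive and half of them by Week 12, about half to two-thirds of first reactions in ADA-positive subjects precede detection when there is no link. A hazard ratio of 3 after seroconversion shows as about 1.7–2.1 instead of about 2.3. Unequal follow-up alone gives 1.05–1.09 under those assumptions, and up to 1.31 with 80% ADA and onset spread over 52 weeks.

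The change is worth making but is not critical. The primary endpoint and the between-arm safety comparison are unaffected.

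**What to change.** Keep the SAP 16.6 tables as they are and add the following, by arm, for hypersensitivity AESIs and injection site reactions:

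1. A table by ADA status at event onset. An event counts as ADA-positive only if it begins on or after the date of the first positive post-dose sample. Earlier events and earlier time count as ADA-negative.
2. Subject-years, and events per 100 subject-years, before and after the first positive sample. Stratify by study period, because crude before-and-after rates are confounded with time if reactions cluster early.
3. The same for NAb.
4. A stated rule for subjects already positive at baseline, whom 16.6 does not separate, and for early-termination samples prompted by the event itself.
5. A sensitivity run that dates ADA onset from the last negative sample.

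The cost is SAP wording and programming on dates already collected. The limits are small event counts per arm and detection known only to intervals of up to 16 weeks, so the added tables should be presented as descriptive.
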